2.0 Introduction

This document presents a Statistical Analysis Plan (SAP) for MAPS study protocol MP-12, a Phase 2 pilot clinical trial designed to evaluate the safety and efficacy of MDMA-assisted psychotherapy in treating chronic, treatment-resistant PTSD.

The statistical plan described hereafter is an *a priori* plan based on the statistical analysis plans included in the study protocol. This SAP will be finalized prior to any unblinded or inferential or descriptive analyses of data pertaining to the MAPS MP-12 study. SAS programming may occur as study data accumulate in order to have analysis programs ready at the time of unblinding of the clinical team. In such an event, arbitrary treatment group assignments must be randomly linked to subjects, effectively rendering any output of programs meaningless. For the reasons stated here the conduct of the study in the field is considered to be independent of any study outcome that might materialize upon enactment of the currently proposed statistical plan.

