4.2 Secondary Objectives

The following objectives will compare each active dose group and the comparator dose group in Stage 1:

- Assess changes in self-reported PTSD symptoms as measured with the PTSD Diagnostic Scale (PDS) at baseline, after each experimental session and/or the primary endpoint.
- Assess depression symptoms with the Beck Depression Inventory-II (BDI-II) at baseline and the primary endpoint.
- Assess global functioning with the Global Assessment of Functionality (GAF) at baseline and the primary endpoint.
- Assess self-reported sleep quality with the Pittsburgh Sleep Quality Index (PSQI) at baseline and the primary endpoint.
- Assess self-reported dissociation symptoms with the Dissociative Experiences Scale II (DES-II) at baseline and the primary endpoint.
- Assess self-reported posttraumatic growth with the Posttraumatic Growth Inventory (PTGI) at baseline and the primary endpoint.

The following objectives will compare effects in specified subjects:

- Assess PTSD symptoms via CAPS and PDS, depression symptoms via BDI-II, global functioning via GAF, sleep quality via PSQI, posttraumatic growth via PTGI, and dissociation symptoms via the DES-II, throughout Stage 2 in comparison to Stage 1 in crossover subjects.
- Assess long-term effects of MDMA-assisted psychotherapy on symptoms of PTSD, depression, and global function, sleep quality, dissociation symptoms via CAPS and PDS, BDI-II, GAF, PSQI, PTGI (in reference to start of the study), and DES-II one year after the final experimental session for each subject.

The following objectives will include exploratory analyses intended to inform future protocol design:

- Explore the effects of each experimental session upon self-reported changes in consciousness, as those associated with a transformational or mystical experience via the States of Consciousness Questionnaire (SOCQ).
- Assess the effect of the third experimental session for active dose subjects in Stage 1 and Stage 2 using CAPS, PDS, BDI-II, GAF, PSQI, PTGI (in reference to start of the study), and DES-II.
- Assess the ability of the investigators and subjects to accurately guess treatment group assignment in Stage 1.
- Correlate adherence to the treatment manual with Global CAPS scores using adherence criteria ratings to assess videos of psychotherapy sessions.

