PTSD symptoms will be assessed throughout Stage 1. For subjects continuing on to Stage 2, PTSD symptoms will be assessed throughout Stage 2. All subjects will complete a follow-up occurring two months after their last experimental session in Stage 1 and Stage 2, if applicable. In addition all subjects will complete a visit 12 months after their final experimental session where outcome measures and a questionnaire on any lasting benefits or harms of the treatment will be administered (see Time and Events Table).

Table 4.0-1: Dose Regimen

Dose	Initial Dose	Optional Supplemental Dose	Min-Max Cumulative Dose	Min-Max Cumulative Dose with Titration
Active Dose 1	125 mg	62.5 mg	125-187.5 mg	N/A
Active Dose 2	100 mg	50 mg	100-150 mg	N/A
Active Dose 2 + Optional Titration Dose	100 mg +25 mg	50 mg +12.5 mg	100-150 mg N/A	N/A 125-187.5 mg
Comparator Dose	40 mg	20 mg	40-60 mg	N/A

Table 2. Time & Events Stage 1	Screen/ Baseline	Preparatory Sessions	Experimental Session 1		Experimental Session 2		Primary Endpoint	Experimental Session 3		End of Stage 1
Visit #	Prior to enrollment	V1,2,3	V4	V5,6,7	V8	V9,10,11	V12	V13 ^N	V14,15,16 ^N	V17 ^N
Type of Visit	Screening	Preparatory	Experimental	Integrative	Experimental	Integrative	Outcome	Experimental	Integrative	Outcome
Visit Timing	Over 2 mo. prior to V1	Appr.1 week apart	3-5 weeks post baseline	Between V4 and V8	3-5 weeks post V4	Between V8 and V12	1 month post V8	After V12	Between V13 and V17	2 months post V13
Initial Phone Screen	✓									
Informed Consent	✓									
Medical/Psychiatric History	✓									
General Physical Exam, ECG	✓									
Brief Neurological Exam	✓									
SCID	✓									
Clinical Lab Tests, w/ HIV test	✓									
Collect Concomitant Medication	✓	✓	✓	✓	✓	✓	✓	✓	✓	✓
Medication Taper (if applicable)		✓								
Study Enrollment if eligible		✓ ^O								
Record to Audio/Video		✓	✓	✓	✓	✓		✓	✓	
General Well-Being		✓	✓	✓	✓	✓	✓	✓	✓	
Drug Screen	✓		✓		✓			✓		
Pregnancy Screen (if applicable)	✓		✓		✓			✓		
Obtain container assignment			✓ ^B		✓ ^B					
CAPS, GAF, BDI-II, PSQI, PTGI, DES-II	✓						✓ ^L			✓
RBANS/PASAT	✓						✓			✓
PDS	✓			✓ ^M			✓		✓ ^M	✓
C-SSRS	✓	✓ ^G	✓ ^{C,D,E}	✓ ^I	✓ ^{C,D,E}	✓ ^I	✓	✓ ^{C,D,E}	✓ ^I	✓
Administer Drug + Therapy			✓		✓			✓		
Monitoring of BP, Pulse, and Temp.			✓		✓			✓		
SUD			✓ ^{E,F}		✓ ^{E,F}			✓ ^{E,F}		
Belief of Condition Assignment				✓ ^K		✓ ^K				
Overnight Stay, SOCQ			✓		✓			✓		
Integrative Therapy Session				✓ ^A		✓ ^A			✓ ^A	

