Seven Days Telephone Contact				✓		✓			✓	
AEs Requiring Medical Attention		✓	✓	✓	✓	✓	✓	✓	✓	✓
Spont. Reported Reactions & all AEs			✓ ^J	✓	✓ ^J	✓	✓	✓ ^J	✓	✓
Changes in Tinnitus and/or Pain	✓ ^P		✓ ^{E,P}	✓ ^{E,P}	✓ ^{E,P}	✓ ^{E,P}	✓ ^P	✓ ^{E,P}	✓ ^{E,P}	✓ ^P
AEs of psychiatric status or withdrawal		✓	✓	✓	✓	✓	✓	✓	✓	✓
Serious Adverse Events		✓	✓	✓	✓	✓	✓	✓	✓	✓

Issue Memory Aid Card										✓ ^H
Unblinding							✓			
Perception of Experimental Sessions							✓ ^N			✓ ^N
RRPQ										✓ ^H

A = First Integrative session is one day after experimental session; B = At least 24 hours prior to experimental session; C = Approximately six hours post MDMA; D = At the beginning of the session; E = As needed; F = Approximately every 60 minutes; G = Given on 2nd preparatory session after washout; H = Only for subjects starting long-term follow-up; I = All visits and Day 2 and Day 7 phone calls only; J = Reactions collected for seven days post experimental session; K = On the day of the first integrative session following the experimental session; L = One month after the second experimental session but before the third experimental session; M = On the day of the third integrative session; N = Active dose subjects only; O = Only on Visit 1; P = Only in subjects with pre-existing tinnitus and/or chronic pain.

Time of Events Stage 2	Preparatory Session	Experimental Session 1		Experimental Session 2		Secondary Endpoint	Experimental Session 3		End of Stage 2	Long-term Follow-up
Visit #	V18*	V19	V20,21,22	V23	V24,25,26	V27	V28	V29, 30, 31	V32	LTFU
Type of Visit	Preparatory	Experimental	Integrative	Experimental	Integrative	Outcome	Experimental	Integrative	Outcome	Follow-up
Visit Timing	Within 1 month post V12*	1 week post V18	Between V19 and V23	3-5 weeks post V19	Between V23 and V27	1 month post V23	1 month post V23	Between V28 and V32	2 months post V28	1 year post V13 or V28
Confirm Informed Consent	✓									
Confirm Inclusion/Exclusion	✓									
Enrollment in Stage 2	✓									
Collect Concomitant Medication	✓	✓	✓	✓	✓	✓	✓	✓	✓	✓
Record to Audio/Video	✓	✓	✓	✓	✓	✓	✓	✓	✓	
General Well-Being	✓	✓	✓	✓	✓	✓	✓	✓	✓	
Drug Screen		✓		✓			✓			
Pregnancy Screen (if applicable)		✓		✓			✓			
CAPS, GAF, BDI-II, PSQ, PTGI, DES-II	Use V12*					✓ ^H			✓	✓
RBANS/PASAT									✓	
PDS	Use V12*		✓ ^I			✓		✓ ^I	✓	✓
C-SSRS	✓	✓ ^{B,C,D}	✓ ^G	✓ ^{B,C,D}	✓ ^G	✓	✓ ^{B,C,D}	✓ ^G	✓	✓
Administer Drug + Therapy		✓		✓			✓			
Monitoring of BP, Pulse, and Temp.		✓		✓			✓			

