6.0 Randomization and Blinding

Per Amendment 6, 26 subjects will be enrolled into the study. The randomized portion of the study will be blinded and there will be a 12:9:5 ratio between subjects in the active dose 1, active dose 2, and comparator dose treatment groups. Subjects will be assigned subject numbers, and subjects will be randomized in a blinded fashion.

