9.2 Handling of Dropouts, Missing Data

Subjects who discontinue treatment prior to completing the second experimental session and the primary endpoint will be replaced. These dropout subjects will be asked to complete an outcome assessment prior to continuing to the long-term follow-up.

Early termination visit data for mITT and Safety variables will be analyzed at the closest scheduled visit after the last experimental session completed. If the closest visit has valid data, the early termination data will be assigned to the next available visit. If a subject discontinues and does not participate in an early termination visit, data from the last available visit will be used to replace the missing early termination visit data.

Partial or Missing Dates:

The following conventions will be used to impute missing portions of dates for adverse events and concomitant medications. Note that the imputed values outlined here may not always provide the most conservative date. In those circumstances, the imputed value may be replaced by a date that will lead to a more conservative analysis.

A. Start Dates

- 1) If the year is unknown, then the date will not be imputed and will be assigned a missing value.
- 2) If the month is unknown, then:
 - i) If the year matches the first dose date year, then impute the month and day of the first dose date.

- ii) Otherwise, assign 'January.'
- 3) If the day is unknown, then:
 - i) If the month and year match the first dose date month and year, then impute the day of the first dose date.
 - ii) Otherwise, assign the first day of the month.

B. Stop Dates

- 1) If the year is unknown, then the date will not be imputed and will be assigned a missing value.
- 2) If the month is unknown, then assign 'December.'
- 3) If the day is unknown, then assign the last day of the month.

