- Here is my suggestion for wording the bullet point above: To determine if baseline variables that assess disassociation are predictive of CAPS Global Severity Score at the Primary Endpoint (dependent variable), a multiple regression analysis will include the following independent variables at baseline (1) dichotomous variable defined as Frequency of 2 or greater and Intensity of 2 or greater on the CAPS Associated Features 29 or the alternative (2) dichotomous variable defined as Frequency of 2 or greater and Intensity of 2 or greater on the CAPS Associated Features 30 or the alternative, and (3) DES-II total score.
-

PTSD Diagnostic Scale (PDS)

A repeated measures analysis of variance (ANOVA) will be performed upon PDS scores at baseline, after experimental sessions (visits 4 and 13) and at the end of Stage 1 (visit 17), with p value set at 0.05. Stage I treatment group will serve as a between-subjects factor. Results of repeated measures ANOVA analysis will be used to examine the effects of each experimental session on self-reported PTSD symptom severity.

Clinician Administered PTSD Scale-4 (CAPS-4) and PTSD Diagnostic Scale (PDS)

PDS and CAPS scores will be correlated via Pearson's product moment correlation at baseline and the timepoint that the primary efficacy is measured to provide a comparison of a self-report measure with a clinician-administered measure of PTSD symptoms.

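### The exploratory PDS repeated-measures ANOVA leaves out V12, so sessions 2 and 3 cannot be separated, and it uses two visits the 40 mg arm does not have

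*SAP*

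**What the plan says.** The PDS paragraph of SAP 9.9.3 sets out a repeated-measures ANOVA at the 0.05 level on "PDS scores at baseline, after experimental sessions (visits 4 and 13) and at the end of Stage 1 (visit 17"). It adds that "Stage I treatment group will serve as a between-subjects factor" and gives the purpose as examining the effect of each dosing session on self-reported severity.

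Other parts of the plan describe a fuller set of occasions:

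- SAP 4.2 has PTSD symptoms "measured with the PTSD Diagnostic Scale (PDS) at baseline, after each experimental session and/or the primary endpoint".
- Protocol 12.0 describes the same ANOVA with a PDS after every session, and SAP 2.0 says the SAP is "based on the statistical analysis plans included in the study protocol".
- The Stage 1 Time & Events table (SAP 5.0; the PDS row is the same in the protocol) schedules the PDS at baseline, within V5-7, at V12, within V14-16, and at V17. The cells for V4, V8, V9-11 and V13 are empty. The footnotes read "M = On the day of the third integrative session; N = Active dose subjects only". Mark M places the two integrative-session assessments at V7 and V16; mark N is on V13, V14-16 and V17.
- Protocol 5.2.6 allows the primary-endpoint visit to serve as the PDS occasion for session 2 only. Protocol 5.2.7 says comparator subjects do not have session 3 or its integrative visits.

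SAP 6.0 gives the size: "Per Amendment 6, 26 subjects will be enrolled into the study", allocated 12:9:5 to 125, 100 and 40 mg.

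**The concern.** There are two separate faults.

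First, V12 is missing from the list. Without it nothing is measured between session 2 and session 3, so the model cannot do what its own paragraph says it is for. The step it does estimate mixes a blinded session with an open-label one, and in the 100 mg arm the open-label session may be given at the higher dose (protocol 2.3).

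Second, the between-subjects factor has three levels, but at the last two of the four occasions one level has no scheduled data. If the ANOVA needs complete subjects, the 40 mg arm disappears, and with it the only low-dose comparison for session 1. SAP 9.2 does not help. Its rule that "data from the last available visit will be used to replace the missing early termination visit data" is for subjects who discontinue, not for visits an arm was never meant to attend.

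**Working it through.** The plan gives no power or sample-size figure for this model, so there is none to reproduce. The check is which effects the listed visits can support.

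**Inputs.** Scheduled PDS (Stage 1 table, marks M and N): 125 mg and 100 mg at baseline, V7, V12, V16 and V17; 40 mg at baseline, V7 and V12. Planned n = 12, 9, 5 (SAP 6.0).

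**Definitions.** Session 1 = V7 − baseline. Session 2 = V12 − V7. Session 3 = V16 − V12.

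**What the schedule supports.** Within-arm effects: 3 (session 1) + 3 (session 2) + 2 (session 3) = 8. Pairwise between-arm contrasts of these: 3 + 3 + 1 = 7.

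**The SAP list (baseline, V7, V16, V17).**
- Arm-by-visit cells with data: 4 + 4 + 2 = 10 of 12.
- Subject-visits: 12×4 + 9×4 + 5×2 = 48 + 36 + 10 = 94 of 26×4 = 104.
- V16 − V7 = session 2 + session 3. A design with an intercept and one indicator per session has rank 3 of 4: session 1 is estimable, and sessions 2 and 3 only as a sum.
- Complete cases: 12/9/0, so 26 falls to 21 (5/26 = 19% lost). Dose df fall from 2 (error 26 − 3 = 23) to 1 (error 21 − 2 = 19). Dose-by-visit df are 1×3 = 3 (error 19×3 = 57).

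**Comparison of options.**

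| Visits used | Cells | Subject-visits | Incomplete subjects kept: within / between | Complete cases: within / between | Complete-case n |
|---|---|---|---|---|---|
| SAP list | 10 of 12 | 94 of 104 | 3 of 8 / 3 of 7 | 2 of 8 / 1 of 7 | 12/9/0 |
| SAP list + V12 | 13 of 15 | 120 of 130 | 8 of 8 / 7 of 7 | 6 of 8 / 3 of 7 | 12/9/0 |
| (a) three arms: baseline, V7, V12; and (b) active arms: all five visits | (a) 9 of 9; (b) 10 of 10 | (a) 78 of 78; (b) 105 of 105 | 8 of 8 / 7 of 7 | 8 of 8 / 7 of 7 | (a) 12/9/5; (b) 12/9 |

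For (a), dose df are 2 (error 23) and dose-by-visit df are 2×2 = 4 (error 23×2 = 46). For (b), dose df are 1 (error 19) and dose-by-visit df are 1×4 = 4 (error 19×4 = 76).

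**Sensitivity to the reading.** SAP 5.0 says "All subjects will complete a follow-up occurring two months after their last experimental session in Stage 1 and Stage 2, if applicable", and protocol 5.2.8(c) mentions comparator subjects who decline Stage 2. If every 40 mg subject had a PDS at V17, the SAP list would fill 11 of 12 cells and 48 + 36 + 15 = 99 of 104 subject-visits. V16 would still be absent, so complete cases stay 12/9/0. With the 9:9:5 allocation in the protocol supplied, complete cases fall from 23 to 18 and dose df from 2, 20 to 1, 16.

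**The case against.** The strongest reply is that this is an editing slip rather than a chosen model. The list immediately above the PDS paragraph in SAP 9.9.3 still contains an unresolved wording suggestion, and the stated aim shows that all sessions were meant. That is probably right, but the text as it stands still specifies the wrong visits.

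The loss of the 40 mg arm depends on complete-case fitting, which the SAP neither states nor rules out. A likelihood-based fit keeps the 40 mg baseline and V7 scores, so all three session 1 contrasts survive. This stands, and the second fault is conditional on it. The first fault is not: no fitting method separates sessions 2 and 3 without V12.

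SAP 9.9 promises descriptive statistics by group, and SAP 9.9.2 tests PDS change from baseline to V12 in all three arms. If PDS means are tabulated at each visit, point estimates for each interval can be read off. What is lost is a planned test with an error term. SAP 9.9.2.1 does not fill that gap, because its Stage 1 comparison of three sessions with two names only the CAPS. SAP 9.0 allows labelled post-hoc analyses, but using that route would make a planned aim post hoc.

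The interval changes are also not clean session effects. The first includes preparatory therapy and, for some subjects, medication taper, and the assessment delays after sessions differ. The counts above therefore say what can be estimated, not how well it can be interpreted.

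Finally, the protocol supplied predates the 12:9:5 allocation, so its section 12.0 may since have changed. The SAP's own schedule and objective carry the point without it.

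**Conclusion.** The concern holds and is minor. As listed, the model cannot estimate session 2 or session 3 separately in any arm, contrary to its stated purpose. It estimates 3 of 8 within-arm effects and 3 of 7 between-arm contrasts, all for session 1. Under complete-case fitting these fall to 2 of 8 and 1 of 7, with no 40 mg subjects.

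This rests on reading the listed visits as V7 and V16, which is an inference because the SAP names dosing visits that have no scheduled PDS. It also rests on the planned 12:9:5. Actual numbers depend on the analysis population, which the SAP does not name for this model; SAP 9.3 reports two replaced withdrawals and three subjects with exclusionary conditions. A 40 mg comparison for session 3 is unavailable by design and is not counted as a loss. The primary CAPS analysis and the secondary PDS test at V12 are unaffected.

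**What to change.** In SAP 9.9.3:

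- (a) Fit the three-arm model with dose-by-visit at baseline, V7 and V12. State the analysis population and whether subjects with incomplete visits are kept.
- (b) Fit a separate model in the 125 mg and 100 mg arms that adds V16 and V17 for session 3. Label it open-label and uncontrolled, and identify the 100 mg subjects who moved to 125 mg.
- (c) Name the PDS assessment visits (V7, V12, V16, V17) in place of the dosing visits.

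A single likelihood-based model with V12 added would also recover every effect, provided the SAP commits to keeping incomplete subjects. The two-model form works under either fit. Changing the list to visits 4, 8 and 13 would restore session 2 but leave the empty 40 mg cells.

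If protocol 12.0 still has its present wording after Amendment 6, clarify it to match. The cost is SAP wording only: the PDS is already scheduled at all these visits, so no new data are needed.

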9.9.3.1 Process Measures

States of Consciousness Questionnaire (SOCQ)

Descriptive statistics will be computed for SOCQ scores completed after each MDMA-assisted psychotherapy session, and SOCQ scores will be compared by initial dose using ANOVA for overall differences and t-tests for pairwise comparisons for each experimental session. The data will be explored for effects of dose on composite and total SOCQ scores.

Long-term Follow-up Questionnaire (LTFU Questionnaire)

The LTFU Questionnaire nominal variables will be described in terms of frequencies and percentages, while ordinal and non-normal continuous variables will be described using sample mean, standard deviations, and range.

Belief of Condition Assignment

In order to compare the therapists', independent raters', and subjects' belief of treatment group to actual MDMA dose received in each blinded session, the number and frequency of correct guesses will be calculated and depicted by dose group and study role (subject and each therapist).

Subject's Perceptions of Experimental Sessions

Descriptive statistics will be calculated for subject's perceptions of experimental sessions. Mean, standard deviation and range of individual responses and sum of items #1-4 will be examined. For the 100 and 125 mg group, within-subjects t-tests will be performed on subject's perceptions at Stage 1 primary (visit 12) and end of stage 1 (visit 17) endpoints. The same analysis will be performed for 40 mg group, but data will be from Stage 2 secondary (visit 27) and end of stage 2 (visit 32) endpoints.

Reactions to Research Participation Questionnaire (RRPQ)

Frequency of response will be tabulated for 'reasons for participation' across Stage 1 treatment groups. Descriptive statistics will be computed for total scores for subscales and displayed by Stage 1 conditions.

Adherence to the Treatment Manual

The sponsor will collect ratings of adherence to the treatment manual from specifically selected types of sessions. Descriptive statistics will be computed for each adherence scale within a given session. If sufficient data is available, the sponsor will correlate the mean adherence ratings for adherence scale and session type with Global CAPS scores from the closest available endpoint assessment to investigate the effects of adherence to the treatment manual on reduction in PTSD symptoms. If it is found that there are specific factors within the adherence scales, then the factor will be correlated with Global CAPS score.

Qualitative Interviews

Qualitative interviews conducted by a researcher who is part of the study team during the 12-month follow-up visit will be transcribed to text. A computer-assisted qualitative data analysis software package will be utilized to assist in thematic content analysis of the interview transcripts. A member of the research team will code the interviews for content, to identify emerging themes and organize data into thematic constructs utilizing a grounded theory approach. Descriptive statistics will be calculated for emerging themes.

